Starting dose: 20 mg/m² for patients ≥ 1 year of age; 15 mg/m² for patients < 1 year of age (Dose Level 1). See Dosing Schema in [Section 5.4](#).***NOTE:** Give MLN4924 (pevoneditat) 30 – 60 minutes after the completion of the azacitidine infusion. If MLN4924 (pevoneditat) dosing is delayed, a minimum of 1 full calendar day between any 2 doses should be maintained.**Fludarabine: IV over 30 minutes once daily**

Days: 6-10

Dose: Age based dosing

Age	Dose
< 1 year	1 mg/kg/dose
≥ 1 year	30 mg/m ² /dose

High Dose Cytarabine: IV infusion over 1-3 hours once daily

Days: 6-10

Dose: Age based dosing (begin 4 hours after start of fludarabine)

Age	Dose
< 1 year	67 mg/kg/dose
≥ 1 year	2000 mg/m ² /dose

Please note: Following/during high-dose cytarabine, chemical conjunctivitis may occur. Administer steroid eye drops (0.1% dexamethasone or 1% prednisolone ophthalmic solution), 2 drops to each eye every 6 hours, beginning immediately before the first dose and continuing for 24 hours after the last dose. If patient does not tolerate steroid eye drops, artificial tears may be administered on an every 2-4 hour schedule.

See the Chemotherapy Administration Guidelines (CAG) on the COG website at: https://cogmembers.org/_files/disc/Pharmacy/ChemoAdminGuidelines.pdf for special precautions and suggestions for patient monitoring during the infusion. As applicable, also see the CAG for suggestions on hydration, or hydrate according to institutional guidelines.

5.3**Criteria for Starting Cycle 2**

Patients may proceed to cycle 2 following completion of cycle 1 disease assessment if stable or greater response and if non-hematologic toxicities probably or definitely related to MLN4924 (pevoneditstat) recover to \leq grade 2. Bilirubin, ALT, and AST must be \leq Grade 1 or at the patient's baseline values prior to starting Cycle 2.

NOTE: See [Appendix III](#) for Toxicity Specific Grading.

- Patients will have disease assessment on Day 36-39 of Cycle 1. If a bone marrow aspirate cannot be evaluated (dry tap, no spicules), a follow-up bone marrow aspirate and biopsy must be performed within 2 weeks to assess cellularity and response.
- If aspirate and/or biopsy results indicate hypocellular marrow (<10% cellularity on biopsy), then continue to repeat bone marrow aspirate and/or biopsy not less than once every 14 days until response can be assessed.

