- If count recovery is noted within 14 days of an unevaluable marrow, there is no need to repeat the marrow to confirm response.
- If the patient meets criteria for CR, CRp, or CRi after Cycle 1 then the patient can proceed to Cycle 2 (See [Section 12.2](#) for definitions of response)
- If the bone marrow aspirate and/or biopsy performed after Cycle 1 reveals $\geq 5\%$ but $\leq 25\%$ blasts, then the patient should proceed to Cycle 2 of chemotherapy

5.4**Dosing Schema****5.4.1 Dose Confirmation Schema**

The starting dose will be 20 mg/m² for patients ≥ 1 year of age (Dose Level 1) with dose levels for subsequent groups of patients as follows:

Dose Level	MLN4924 (Pevonedistat) Dose (mg/m ²)
-1	15 mg/m ²
1*	20 mg/m²

* Starting Dose Level

The starting dose will be 15 mg/m² for patients < 1 year of age (Dose Level 1) with dose levels for subsequent groups of patients as follows:

Dose Level	MLN4924 (Pevonedistat) Dose (mg/m ²)
-1	10 mg/m ²
1*	15 mg/m²

* Starting Dose Level

There will be no escalations beyond Dose Level 1 (20 mg/m²), as adult studies examining doses higher than 20 mg/m² observed excess toxicity without any apparent disease benefit and no significant differences in pharmacokinetic parameters to suggest significant increase in efficacy.²⁴

If the maximally tolerated dose (MTD) has been exceeded at the first dose level, then the subsequent cohort of patients will be treated at Dose Level -1. If Dose Level -1 is not well tolerated, further de-escalation will not occur. The study will be closed to accrual.

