10.0 CRITERIA FOR REMOVAL FROM PROTOCOL THERAPY AND OFF STUDY CRITERIA

10.1 Criteria for Removal from Protocol Therapy

- a) Evidence of treatment failure (See [Section 12.2.5](#)).
- b) Adverse Events requiring removal from protocol therapy (See [Section 6](#)).
- c) Refusal of protocol therapy by patient/parent/guardian
- d) Non-compliance that in the opinion of the investigator does not allow for ongoing participation.
- e) Completion of 2 cycles of therapy.
- f) Physician determines it is not in the patient's best interest.
- g) Repeated eligibility laboratory studies (CBC with differential, bilirubin, ALT (SGPT) or serum creatinine) are outside the parameters required for eligibility prior to the start of MLN4924 (pevonodistat) (See [Section 8.1](#)).
- h) Study is terminated by Sponsor.
- i) Pregnancy

Patients who are removed from protocol therapy during Cycle 1 should continue to have the required observations in [Section 8.1](#) until the originally planned end of the cycle or until all adverse events have resolved per [Section 13.4.4](#), whichever happens LATER. The only exception is with documentation of the patient's withdrawal of consent. Patients who are removed from protocol therapy in subsequent cycles should have the necessary observations to ensure adequate clinical care.

Patients who are off protocol therapy are to be followed until they meet the criteria for Off Study (see below). Ongoing adverse events, or adverse events that emerge after the patient is removed from protocol therapy, but within 30 days of the last dose of investigational agent, must be followed and reported via RAVE and CTEP-AERS (if applicable). Follow-up data will be required unless consent is withdrawn.

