12.2.4 Partial Response

Attainment of M2 marrow status (\geq 5% or $<$ 25% blasts cells and adequate cellularity) and at least 50% decrease in bone marrow blast percent from baseline. Bone marrow must have adequate cellularity (e.g. \geq 10% if a biopsy is performed) to determine response. PR status will not be included in the calculation of response to the regimen. A repeat bone marrow aspiration within 14 days may be required to distinguish between a PR and increased blasts caused by bone marrow regeneration, and is left to the discretion of the investigator.

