12.2.5 Treatment Failure

The definition of treatment failure includes:

- A. An increase in the extent of bone marrow infiltration by leukemic cells (absolute increase of \geq 20% blasts) OR
- B. Development of extramedullary disease (EMD) OR
- C. M2 marrow that does not qualify for PR status OR
- D. An M1 marrow with circulating blasts OR
- E. $>$ 25% blasts in the bone marrow after Cycle 1 of therapy
- F. Subjects who have persistent CNS disease despite 6 doses of IT cytarabine or IT triples

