One copy of this Pharmacodynamic Study Form should be uploaded into RAVE. A second copy should be sent with the samples to the address listed in [Section 8.4.6](#). See [Section 8.4](#) for detailed guidelines for packaging and shipping PD – mRNA Transcript Level samples.

Signature: _____ Date: _____
(site personnel who collected samples)

THIS PROTOCOL IS FOR RESEARCH PURPOSES ONLY, SEE PAGE 1 FOR USAGE POLICY

**APPENDIX VII: PHARMACODYNAMICS (NEDDYLATED PROTEIN ANALYSIS) STUDY
FORM – BONE MARROW SAMPLES**COG Pt ID # _____ Cycle 1, Day 1 Date: _____
Please do not write patient names on this form or on samples.Patient Weight: _____ kg Body Surface Area: _____ m²MLN4924 (Pevonedistat) Dose Level: _____ mg/m² MLN4924 (Pevonedistat) Total Daily Dose: _____ mg

WBC: _____ /µL % Blasts: _____ %

In consenting patients, bone marrow samples (2-3 ml) will be collected in heparinized tubes at the following time points: pre-study, and at the end of Cycle 1 on the same day as bone marrow evaluation.

Record the exact time the sample is drawn.

Blood Sample No.	Time Point	Scheduled Collection Time	Actual Date Sample Collected	Actual Time Sample Collected (24-hr clock)
1	Pre-study	Pre-study	____ / ____ / ____	____ ____ : ____ ____
2	End of Cycle 1	Same day as bone marrow evaluation	____ / ____ / ____	____ ____ : ____ ____

One copy of this Pharmacodynamic Study Form should be uploaded into RAVE. A second copy should be sent with the samples to the address listed in [Section 8.4.6](#). See [Section 8.4](#) for detailed guidelines for packaging and shipping PD – mRNA Transcript Level samples.

Signature: _____ Date: _____
(site personnel who collected samples)

THIS PROTOCOL IS FOR RESEARCH PURPOSES ONLY, SEE PAGE 1 FOR USAGE POLICY

APPENDIX VIII-A: THERAPY DELIVERY MAP FOR CYCLE 1

Therapy Delivery Map – Cycle 1

This Therapy Delivery Map (TDM) relates to Cycle 1. Each cycle lasts 35 days.

Patient COG ID number

DOB

Criteria to start each cycle are in [Section 5.3](#). Extensive treatment details are in [Section 5.2](#).

This TDM is on 4 pages.

DRUG	ROUTE	DOSAGE	DAYS	IMPORTANT NOTES
IT Cytarabine (ARAC) (all patients)	Intrathecal (IT)	Age-based dosing: Age (yrs) Dose < 1 20 mg 1-1.99 30 mg 2-2.99 50 mg ≥ 3 70 mg	0	Given at the time of diagnostic lumbar puncture OR Day 0.

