- m. CSF for cell count, cytospin. Prior to Cycle 1 and at the end of Cycle 1.
- n. Pharmacodynamics (mRNA Transcript Levels). Optional samples to be collected on day 1 pre-MLN4924 (pevoneditstat) dose and on day 3 **OR** day 5 at 3 hours and 6 hours after the end of MLN4924 (pevoneditstat) infusion. See [Section 8.3](#) for details.
- o. Pharmacodynamics (NEDDylated Protein Analysis). Optional samples to be collected on day 1 pre-MLN4924 (pevoneditstat) dose, and at 10 hours and 24 hours after the end of MLN4924 (pevoneditstat) infusion. An additional sample is to be collected at the end of Cycle 1 on the same day as bone marrow evaluation. See [Section 8.4](#) for details.
- p. ALT, AST, Bilirubin. Prior to Cycle 1, prior to each dose of MLN4924 (pevoneditstat), and then weekly.

ADVL1712

THIS PROTOCOL IS FOR RESEARCH PURPOSES ONLY, SEE PAGE 1 FOR USAGE POLICY

q. Vital signs. Prior to each dose of MLN4924 (pevonodistat).

This listing only includes evaluations necessary to answer the primary and secondary aims. OBTAIN OTHER STUDIES AS REQUIRED FOR GOOD CLINICAL CARE.

Comments

(Include any held doses, or dose modifications)

Cycle 1

APPENDIX VIII-B: THERAPY DELIVERY MAP FOR CYCLE 2

Therapy Delivery Map – Cycle 2
 
This Therapy Delivery Map (TDM) relates to Cycle 2. Each cycle lasts 35 days.
	
Patient COG ID number _____
 
DOB _____

---	---

Criteria to start each cycle are listed in [Section 5.3](#). Extensive treatment details are in [Section 5.2](#).

This TDM is on 3 pages.

DRUG	ROUTE	DOSAGE	DAYS	IMPORTANT NOTES
IT Cytarabine (ARAC) (all patients)	Intrathecal (IT)	Age-based dosing: Age (yrs) Dose < 1 20 mg 1-1.99 30 mg 2-2.99 50 mg ≥ 3 70 mg	0	Given at the time of bone marrow aspirate/biopsy at the end of Cycle 1 OR on Day 0 of Cycle 2. See Section 5.2 and Section 5.3 for full details.
Azacitidine (AZA)	IV over 15 minutes	Age-based dosing: Age (yrs) Dose < 1 2.5 mg/kg/dose ≥ 1 75 mg/m ² /dose	1-5	On days 1, 3, and 5, administer before MLN4924 (pevoneditat) infusion. See timing below.
MLN4924 (Pevonedistat)	Intravenous (IV) over 1 hour	Patients < 1 year of age: Dose Level -1: 10 mg/m ² Dose Level 1: 15 mg/m ² Patients ≥ 1 year of age: Dose Level -1: 15 mg/m ² Dose Level 1: 20 mg/m ²	1, 3, 5	Administer 30-60 minutes after completion of azacitidine.
Fludarabine (FLU)	IV over 30 minutes	Age-based dosing: Age (yrs) Dose < 1 1 mg/kg/dose ≥ 1 30 mg/m ² /dose	6-10	

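### Sections 5.3 and 12.2.5C with 10.1(a) give opposite instructions for a post-Cycle 1 marrow of 5–25% blasts with less than a 50% fall from baseline

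*Combined protocol and SAP*

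**What the plan says.** Five provisions of the protocol bear on the same marrow result.

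- **5.3, lead sentence.** Cycle 2 is open after the Cycle 1 disease assessment "if stable or greater response", subject to recovery of related non-hematologic toxicity and of liver values.
- **5.3, last bullet.** With at least 5% and at most 25% blasts after Cycle 1, "then the patient should proceed to Cycle 2 of chemotherapy".
- **12.2.4.** A PR is an M2 marrow with adequate cellularity and "at least 50% decrease in bone marrow blast percent from baseline". Section 12.2.8 sets M2 at 5–25% blasts, the same range as the 5.3 bullet.
- **12.2.5C.** Treatment failure includes an "M2 marrow that does not qualify for PR status". No cycle is named.
- **10.1.** Item (a), "Evidence of treatment failure", cites 12.2.5 and is a reason to stop protocol therapy. Item (e) is "Completion of 2 cycles of therapy".

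Sections 5.3, 10.1 and 12.2.5 contain no exception in favour of one another.

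**The concern.** A child whose marrow improves, but by less than half, and lands in the M2 range is told by one section to have Cycle 2 and by two others to stop. Two sites could each follow the protocol as written and treat the same result differently.

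The decision is clinically heavy, because Cycle 2 repeats azacitidine, pevonedistat, fludarabine and high-dose cytarabine. It also determines which patients contribute Cycle 2 toxicity data and have a second chance to reach remission, so both descriptive summaries would depend partly on how sites resolved the contradiction.

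**Working it through.** The plan has no figure to reproduce here. The check applies each rule to the same pair of values.

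**Notation.** b = baseline marrow blast %, p = marrow blast % after Cycle 1. Adequate cellularity is assumed, and the other 5.3 conditions are taken as met.

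**Rules**
- 5.3 bullet: proceed if 5 ≤ p ≤ 25.
- 12.2.4: the PR fall condition is (b − p)/b ≥ 50%, that is, p ≤ b/2.
- 12.2.5C with 10.1(a): stop if 5 ≤ p ≤ 25 and the marrow is not a PR.
- Conflict from the fall condition: 5 ≤ p ≤ 25 and p > b/2.

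**Single cases**

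| b to p | Fall | PR? | 5.3 bullet | 12.2.5C + 10.1(a) |
|---|---|---|---|---|
| 30 to 20 | 10/30 = 33.3% | no | proceed | stop |
| 20 to 15 | 5/20 = 25.0% | no | proceed | stop |
| 8 to 6 | 2/8 = 25.0% | no | proceed | stop |
| 40 to 20 | 20/40 = 50.0% | yes | proceed | no objection |
| 60 to 20 | 40/60 = 66.7% | yes | proceed | no objection |

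For 30 to 20, the other marrow-percentage items in 12.2.5 are not met: item A needs a rise of at least 20 percentage points, and item E needs more than 25%. Item C alone creates the clash.

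**Which baselines are affected.** If blasts have not risen, the conflict window runs from the larger of 5 and just above b/2, up to the smaller of b and 25.

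| Baseline | Conflicting p, no rise |
|---|---|
| 8% | 5–8% |
| 12% | >6–12% |
| 20% | >10–20% |
| 30% | >15–25% |
| 40% | >20–25% |
| 50% or more | none from the fall condition, since b/2 ≥ 25 |

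If b < 10 then b/2 < 5, so no marrow in the M2 range can be a PR and every 5–25% result conflicts. Such baselines are eligible: 4.1.2.1 admits relapse at 5% marrow blasts, and at lower levels with flow cytometric, cytogenetic or molecular evidence.

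**Where p is above b** (for example 2 to 10), the bullet and 12.2.5C still disagree on their face. Here, though, the undefined condition in the 5.3 lead sentence can be read to hold the patient back.

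**Where 12.2.5C has force.** Item 10.1(e) already ends protocol therapy after two cycles. As a stopping rule, 12.2.5C therefore matters mainly after Cycle 1, which is where it meets the 5.3 bullet.

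**The case against.** **Section 5.3 is the specific rule and plainly governs.** This is the strongest reply. Both Therapy Delivery Maps send the site there ("Criteria to start each cycle are in" section 5.3 in Appendix VIII-A; "Criteria to start each cycle are listed in" section 5.3 in VIII-B). The lead sentence accepts less than a response, and the bullet says such patients should go on. That supports a modest lean and no more. Stable is not defined, and 12.2 has no stable-disease category. A site could read it as not being a treatment failure, which strains the bullet but points the other way. The maps refer to the whole of 5.3, including that condition.

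**12.2.5E shows the intent, because it is the only marrow item tied to Cycle 1.** A reader might infer that C was meant for later. The ranges do not support this: C covers 5–25% and E covers more than 25%. They do not overlap, and together they fit a scheme in which both apply after Cycle 1.

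**12.2.5C is only a response label.** It carries no such limit, and 10.1(a) uses 12.2.5 to stop treatment. Section 5.2 does the same for persistent CNS disease.

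**A repeat marrow resolves it.** The repeat in 12.2.4 is discretionary and helps when regeneration is suspected. Once the marrow is judged M2 and not PR, the conflict remains.

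**The impact is small.** This stands in part. Response is a secondary aim reported descriptively (1.2, 11.5), and 12.2.4 leaves PR out of the response calculation. The PR boundary therefore matters only through who receives Cycle 2. Divergence between sites is possible, not shown.

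**Conclusion.** The contradiction is real and should be fixed. It covers post-Cycle 1 marrows of 5–25% blasts with less than a 50% fall, including every such marrow when baseline is below 10%. Confidence is high for the conflict and only modest for the view that 5.3 was meant to prevail. How many patients would be affected cannot be said. The experimental design schema figure could not be read for this review, so the absence of an exception is judged on the text alone.

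Three stronger readings are not supported:

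- **Dose finding is compromised.** It is not. DLT and MTD are defined on Cycle 1 (5.6, 11.2.2), and the RP2D rule in 11.3 counts those DLTs.
- **A marrow of exactly 25% can never be a PR.** That requires reading the or in the 12.2.4 blast range as and. The text shows garbled drafting, not an established exclusion.
- **Stable must mean no rise at all.** Nothing sets that threshold. Item 12.2.5A uses a rise of at least 20 percentage points, and 12.2.4 and 12.2.6 recognise that regeneration can raise blasts. A zero-rise rule would stop a child going from 20% to 21% while one staying at 20% continued.

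**What to change.** Make one rule govern after Cycle 1. The sponsor should choose between:

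1. **Continue without PR.** Limit 12.2.5C to the end-of-Cycle 2 assessment, so that 5.3 decides after Cycle 1. Downside: some patients with less than a 50% fall receive a second intensive cycle, as 5.3 already directs.
2. **Require PR.** Add to the 5.3 bullet that the marrow must also meet PR. Downside: patients with a baseline below 10% can then never proceed on an M2 marrow, because PR is out of their reach.

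Separately, change the PR blast range in 12.2.4 to ≥5% and ≤25%, to match M2 in 12.2.8.

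Neither option settles what stable means. If the sponsor defines it, the threshold needs its own clinical justification; none is proposed here.

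The cost is a wording amendment to 12.2.4 and to either 12.2.5C or 5.3. It needs no extra patients or procedures, since 8.1 already requires the end-of-Cycle 1 marrow.

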5.4.2 Intra-Patient Escalation

Intra-patient dose escalation is not allowed.

5.5 **Grading of Adverse Events**

Adverse events (toxicities) will be graded according to the NCI Common Terminology Criteria for Adverse Events (CTCAE) version 5.0. All appropriate treatment areas should have access to a copy of the CTCAE version 5.0. A copy of the CTCAE version 5.0 can be downloaded from the CTEP website (http://ctep.cancer.gov/protocolDevelopment/electronic_applications/ctc.htm). Any suspected or confirmed dose-limiting toxicity should be reported immediately (within 24 hours) to the Study Chair.

5.6 **Definition of Dose-Limiting Toxicity (DLT)**

DLT will be defined as any of the following events that are possibly, probably or definitely attributable to protocol therapy. The DLT observation period for the purposes of dose-confirmation will be the first cycle of therapy.

Dose limiting hematological and non-hematological toxicities are defined differently.

5.6.1 Non-hematological dose-limiting toxicity:

5.6.1.1 All Grade 3 or greater non-hematological toxicity not clearly related to the underlying disease and attributable to protocol therapy will be considered a DLT except:

- Grade 3 or 4 elevation of ALT/AST that returns to Grade ≤ 1 within 14 days. NOTE: For the purposes of this study the ULN for ALT is defined as 45 U/L regardless of baseline and for AST is defined as 50 U/L regardless of baseline. See [Appendix III](#) for values that represent thresholds between CTCAE grades.

THIS PROTOCOL IS FOR RESEARCH PURPOSES ONLY, SEE PAGE 1 FOR USAGE POLICY

- Grade 3 or 4 electrolyte abnormalities that resolve, with or without supplementation intervention, to \leq Grade 2 within 72 hours. Electrolyte supplementation is encouraged.
- Grade 3 arthralgia/myalgia that returns to Grade \leq 2 within 5 days on analgesics
- Grade 3 or 4 fever, febrile neutropenia, or infection with or without hospitalization
- Grade 3 tumor lysis syndrome
- Alopecia
- Grade 3 maculo-papular or morbilliform rash that resolves to \leq Grade 2 within 7 days
- Grade 3 mucositis that resolves (with or without supportive care) to \leq Grade 2 within 14 days
- Grade 3 fatigue or anorexia responsive to supportive care within 7 days
- Grade 3 nausea, vomiting, and/or diarrhea responsive to supportive care within 72 hours
- Early intervention with TPN or enteral tube feeding for anorexia, nausea, or concern for poor nutritional status

5.6.2 Hematological dose-limiting toxicity:

Hematological dose limiting toxicity attributable to protocol therapy is defined as failure to recover to a peripheral ANC $> 500/\text{m}^3$ and platelets $> 20,000/\text{mm}^2$ by 50 days from the start of fludarabine and cytarabine administration, not due to presence of leukemia or severe infection (defined as Grade ≥ 3).

- **NOTE:** Grade 3 or 4 febrile neutropenia will not be considered a dose-limiting toxicity

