Regimens used in relapsed AML are very intensive with known toxicities, especially myelosuppression. Given the intensity of myelosuppression for many relapsed AML regimens, there is no consensus measure of what duration is excessively toxic. Recent review of the COG trial AAML0531 is in line with TACL's findings, as on this study the median time to platelet > 50,000 and ANC > 500 was 38 and 37 days, respectively, and evaluation of approximately 2 standard deviations of this is approximately 50 days. More recent COG trials for relapsed AML, including the current first line relapse trial, have set a duration of greater than 50 days from the start of therapeutic cycle as excessively myelosuppressive and a DLT based on the recovery times for multi-agent intensive regimens. Fludarabine and cytarabine is comparable in intensity to this regimen, therefore for this trial a time of 50 days from the start of therapy without hematologic recovery (ANC>500 and a non-transfusion platelet count > 20,000) as a hematologic DLT.

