NOTE: Central venous access in the form of a double lumen Broviac or Hickman is highly recommended.

	Day 0	1	2	3	4	5	6	7	8	9	10	11-34	35
IT Cytarabine (all patients)	X												
Azacitidine		X	X	X	X	X							
MLN4924 (Pevonedistat)		X		X		X							
Fludarabine							X	X	X	X	X		
Cytarabine							X	X	X	X	X		
IT Cytarabine OR ITT* (CNS2/3)									X*			X*	

*For patients with CNS 2/3 status, IT cytarabine or ITT should be administered 2x/weekly until the CNS is clear of blasts on 2 consecutive LPs, with a minimum of 4 IT cytarabine/IT triple doses administered. This should begin on Day 8 and should be repeated 2x/weekly with not less than 3 days between doses, thus any necessary subsequent doses should be given starting on Day 11. Days of therapy may vary depending on scheduling.

A cycle of therapy is considered to be 35 days. A cycle may be repeated for a total of 2 cycles, up to a total duration of therapy of approximately 4 months.

Drug doses of MLN4924 (pevonedistat), azacitidine, fludarabine, and cytarabine should be adjusted based on the BSA calculated from height and weight measured within 7 days prior to the beginning of each cycle. Drug doses of intrathecal cytarabine and intrathecal triples should be based on the age at the time of administration.

See [Appendix VIII](#) for Therapy Delivery Maps for each cycle.

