6.1 Dose Modifications for Hematological Toxicity

6.1.1 Patients who experience a hematologic dose limiting toxicity (see [Section 5.6.2](#)), defined as failure to recover peripheral ANC $> 500/\text{uL}$ and non-transfusion dependent platelet count $> 20,000/\text{uL}$ due to documented bone marrow aplasia/hypoplasia (not due to malignant infiltration or Grade 3 infection) for greater than or equal to 50 days from the start of fludarabine and cytarabine administration, will be allowed to proceed at the discretion of the treating physician and study chair with cycle 2 at MLN4924 (pevonedistat) dose level -1. The patient's dose for azacitidine, fludarabine, and cytarabine will remain unchanged.

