11.2.2 Maximum Tolerated Dose

- The MTD will be the maximum dose at which fewer than one-third of patients experience DLT (See [Section 5.6](#)) during Cycle 1 of therapy.
- In the unlikely event that two DLTs observed out of 6 evaluable patients are different classes of Adverse Effects (e.g. hepatotoxicity and myelosuppression), AND all of the following conditions are met, expansion of the cohort to 12 patients will be considered:
 - One of the DLTs does not appear to be dose and/or drug-related
 - The Adverse Effects are readily reversible
 - The study chair, DVL statistician, DVL committee chair or vice chair, and IND sponsor all agree that expansion of the cohort is acceptable
- The DLTs observed in the pharmacokinetic (PK) expansion cohort will be counted towards the total number of DLTs observed at the RP2D/MTD during the dose confirmation portion of the study. If $\geq 1/3$ of the cohort of patients at the RP2D/MTD (during the dose confirmation plus the PK expansion) experience DLT then the MTD will be exceeded.

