11.3 Dose Confirmation and Determination of MTD/RP2D

The rolling six phase 1 trial design will be used for the conduct of this study.³² There is no dose escalation beyond DL1 (20 mg/m²); but the R6 logic will be used to determine the MTD/RP2D. DL1 will be defined as the RP2D if there are less than or equal to 1 patient(s) with a DLT among up to six evaluable patients. Otherwise, DL-1 will open to accrual of up to six evaluable patients. DL-1 will be defined as the MTD/RP2D if there are less than or equal to 1 patient(s) with a DLT among six evaluable patients. Otherwise, DL-1 will have exceeded the MTD and the study will close to accrual without having defined an MTD/RP2D.

In addition to determination of the RP2D/MTD, a descriptive summary of all toxicities will be reported.

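### Hematologic DLT is judged at about Day 56, some three weeks after the 35-day DLT window closes, and no follow-up or evaluability rule closes the gap

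*Combined protocol and SAP*

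**What the plan says.** - **Window.** Section 5.6: "The DLT observation period for the purposes of dose-confirmation will be the first cycle of therapy". Section 11.2.2 ties the MTD to the same period: "The MTD will be the maximum dose at which fewer than one-third of patients experience DLT" during Cycle 1.
- **Cycle length.** Section 5.1: "A cycle of therapy is considered to be 35 days".
- **Hematologic DLT.** Section 5.6.2 judges recovery of ANC and platelets "by 50 days from the start of fludarabine and cytarabine administration". Section 6.1.1 describes non-recovery "for greater than or equal to 50 days from the start of fludarabine and cytarabine administration". Sections 5.1 and 5.2 start both drugs on Day 6.
- **A different anchor.** Section 2.1 gives "for this trial a time of 50 days from the start of therapy without hematologic recovery" as the criterion. Sections 2.1 and 6.1.1 attach a transfusion condition to the platelet threshold; Section 5.6.2 does not.
- **Decision rule.** Section 11.3, for a cohort of at most six evaluable patients: "DL1 will be defined as the RP2D if there are less than or equal to 1 patient(s) with a DLT".

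**The concern.** Hematologic DLT is one of the two DLT components behind the primary tolerability aim, in a four-drug regimen where myelosuppression is the expected toxicity. If the window ends on Day 35 and the event can only be declared around Day 56, the component cannot contribute to the dose decision as written. Only non-hematologic DLTs would then count toward the at-most-1-in-6 rule. If the window was meant to run longer, the plan still has to say how long, keep patients under observation until then, and say what happens to those whose counts are never assessed at the time point. Leaving hematologic DLTs out, or counting unassessed patients as free of DLT, makes the dose look better tolerated than it is.

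**Working it through.** **Calendar.** Inputs: cycle end Day 35 (5.1); fludarabine and cytarabine start Day 6 (5.1, 5.2); last Cycle 1 pevonedistat dose Day 5 (5.1).

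- Anchor of 5.6.2 and 6.1.1: 6 + 50 = Day 56; 56 − 35 = 21 days after the window. If the start day counts as day 1, it is Day 55 and 20 days.
- Anchor of 2.1: 1 + 50 = Day 51; 51 − 35 = 16 days (Day 50 and 15 days if counted inclusively).

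The time point falls after Day 35 under every reading of the anchor.

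**Does another rule close the gap?**

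- *Off study (10.2a).* Thirty days after the last investigational dose is 5 + 30 = Day 35 for a patient who gets no Cycle 2. That precedes the Day 36-39 disease assessment in 5.3. It also conflicts with 10.1, which continues observation until adverse events resolve for patients removed during Cycle 1.
- *Blood counts (8.1, Appendix VIII).* CBCs are twice weekly in Cycle 1, then once before Cycle 2. Apart from the 10.1 extension, none is scheduled between Day 35 and the time point.
- *Cycle 2 entry (5.3).* It requires non-hematologic recovery but sets no count criterion, and CRi qualifies. A patient may be re-exposed before Cycle 1 hematologic status is known.
- *Evaluability (11.2.1).* It requires dose received and appropriate toxicity monitoring. It does not say that hematologic status must be known, so an unassessed patient can count as a non-DLT.

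**How common is late recovery?** For a regimen it treats as comparable in intensity, Section 2.1 reports that "the median time to platelet > 50,000 and ANC > 500 was 38 and 37 days", for platelets and ANC respectively, and puts about 2 SD at 50 days. If this applies here, about half of patients have not reached ANC > 500 at Day 37. For ANC, SD ≈ (50 − 37)/2 = 6.5 days. Assuming normality:

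- P(time > 50 days) = 1 − Φ((50 − 37)/6.5) = 1 − Φ(2.00) = 0.023
- P(time > 55 days) = 1 − Φ((55 − 37)/6.5) = 1 − Φ(2.77) = 0.003

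The second figure corresponds to Day 56 if recovery is timed from Day 1.

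**Effect on the decision rule.** Let n be the non-hematologic and h the hematologic DLT rate, assumed independent. The combined rate is p = 1 − (1 − n)(1 − h), and P(accept) = P(X ≤ 1) with X ~ Binomial(6, p). For example, n = 0.15 and h = 0.10 give p = 1 − 0.85 × 0.90 = 0.235 and P(accept) = 0.570. The documents give no DLT rate for this regimen: all values of n, and h = 0.10 and 0.20, are assumptions.

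| n | Hematologic DLT not counted | h = 0.023 counted | h = 0.10 counted | h = 0.20 counted |
|---|---|---|---|---|
| 0.05 | 0.967 | 0.936 | 0.788 | 0.558 |
| 0.15 | 0.776 | 0.730 | 0.570 | 0.378 |
| 0.25 | 0.534 | 0.494 | 0.368 | 0.233 |

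At n = 0.15 and h = 0.003 the counted figure is 0.770. The uncounted column is the literal case, in which every hematologic DLT falls outside the window.

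**The case against.** The strongest reply is that the authors plainly meant Cycle 1 to last until recovery or the next cycle. Section 5.3 places an assessment on Days 36-39 of Cycle 1. Section 5.1 allows about 4 months for two cycles, which fits 2 × 56 = 112 days (3.7 months) better than 2 × 35 = 70 days (2.3 months). Section 6.1.1 treats aplasia of 50 days or more as a DLT occurring before Cycle 2, and Section 12.2.7 repeats marrow evaluation through at least Day 60. The literal reading would make 5.6.2 empty. All of this is good evidence of intent, but no passage extends the DLT window, and Section 5.1 fixes the cycle at 35 days. The Day 60 rule concerns marrow response, not counts for DLT, and the 10.1 extension covers only patients removed during Cycle 1.

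A second reply is that a patient without counts at the time point could be judged inevaluable under 11.2.1 and replaced. The text permits this but does not require it. Replacing unrecovered patients would also remove those at highest risk of hematologic DLT, which again favours the dose.

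Two points stand. CRi means ANC below 1000 or platelets below 100,000 (12.2.3), while DLT recovery needs only ANC above 500 and platelets above 20,000. Many CRi patients may therefore already have recovered, and the problem is confined to those who start Cycle 2 below the DLT thresholds. The effect on the rule is also negligible at the 0.3% rate. The 2 DLTs among 55 adults at 20 mg/m² (Section 2.3.1; 3.6%, a different regimen) lie nearest the 5% row, where counting a 2.3% hematologic rate moves acceptance only from 97% to 94%.

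**Conclusion.** The concern holds and should be corrected before the dose decision. The window and the hematologic DLT definition contradict each other by 21 days, or by 16 days with the Section 2.1 anchor. This part is calendar arithmetic and needs no assumption. The intended reading can be inferred, but the follow-up and evaluability rules do not support it, so two competent readers could reach different DLT counts from the same patients.

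The size of the effect on the RP2D decision is uncertain. At an assumed 15% non-hematologic rate, acceptance is overstated by under 1 percentage point if hematologic DLT occurs in 0.3% of patients, and by about 5, 21 and 40 points at 2.3%, 10% and 20%. These figures assume independence and that every hematologic DLT is missed. The two small rates also assume normality and that the recovery times cited in Section 2.1 carry over. The effect is small if hematologic DLT is rare and large if adding pevonedistat prolongs aplasia, which is among the things the trial is meant to find out.

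**What to change.** 1. In 5.6 and 11.2.2, state that for the hematologic component the DLT observation period runs until count recovery or the protocol's own hematologic DLT time point, whichever comes first.
2. Reconcile 2.1, 5.6.2 and 6.1.1 to one anchor date and one platelet definition, including whether the transfusion condition applies. The choice is the sponsor's.
3. Reconcile 10.2(a) with 10.1, 5.3 and the DLT window, so that DLT and response follow-up is complete before a patient goes off study.
4. In 8.1 and Appendix VIII, record CBCs from Day 35 until recovery or the DLT time point.
5. In 11.2.1, state how patients who start Cycle 2 or other therapy unrecovered before that point are classified for DLT evaluability.

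The cost is amendment wording and the recording of blood counts after Day 35. DLT status becomes final about three weeks later, but only for patients not yet recovered at Day 35.
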